4.4.3 Prohibited Food

Use of the following foods is prohibited during the study and for at least 7 days prior to initiation of study treatment: furanocoumarin derivatives as found in grapefruit, Seville orange, pomegranate, or star fruit juice or products.

4.4.4 Additional Restrictions

Patients should be fasting for ≥ 4 –8 hours prior to first PK draw at Days 1, 28, and 84. On Day 28, patients should also remain fasting for the 2-hour *post-dose* PK timepoint (see [Appendix 3](#)).

4.5 STUDY ASSESSMENTS

Please see [Appendix 1](#) and [Appendix 2](#) for the schedules of assessments to be performed during this study.

The screening visit can occur up to 28 days prior to the first dose of study drug. The Day 1 (baseline and randomization) visit occurs on the first day of study drug administration.

Morning visits are strongly recommended for the clinic visits on Days 1, 28, and 84, particularly for the Day 28 visit at which post-dose PK blood samples will be collected. Patients should be fasting (≥ 4 –8 hours) prior to these clinic visits. Study drug will be administered at these visits after pre-dose blood samples are collected when applicable. If a morning visit is logistically challenging, then based on the timing of their scheduled visit and scheduled dose, patients may be asked to take their morning dose of study drug as scheduled, then fast (≥ 4 –8 hours) prior to their clinic visit later in the day. At the clinic visit, pre-dose blood samples will be collected and the evening dose of oral study drug will be administered if applicable (e.g., for the Day 28 visit when post-dose blood samples are collected).

Patients who complete the treatment period should complete the Day 84 treatment completion visit (see [Appendix 1](#) and [Appendix 2](#)). After the Day 84 visit is completed, patients who are eligible and consent are to enroll into the OLE Study GA30067 directly; they will not enter the 8-week safety follow-up phase of this study. Patients not eligible

or who choose not to enroll in the OLE study should return for the 8-week safety follow-up visit in this study.

At applicable sites (U.S. only), if the patient is unable to return to the clinic on Day 28 for the PK blood draw at the 8–10 hour timepoint (see [Appendix 3](#)), then this sample may be collected by a home nurse (HN) professional at the patient's home or another suitable location to improve access and convenience for patients participating in the study. If a home visit is needed, the Sponsor will select and provide a health-care company that will be responsible for providing HN services (the HN vendor). The HN vendor is responsible for ensuring that all HN professionals are licensed, qualified, and in good standing, as per applicable regulations, and that appropriate background checks have been performed. If the investigator at a participating site determines that HN services are appropriate for a patient and the patient gives written informed consent to participate in HN visits, the HN network will communicate with the patient and the patient's site. HN visits will be scheduled on specified visit days, to allow for relevant assessments to be performed by the HN professional. The schedule of assessments (see [Appendix 3](#)) specifies the assessment that may be performed by an HN professional.

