4.3.2 Dosage, Administration, and Compliance

4.3.2.1 GDC-0853 and Placebo Dose and Administration

The GDC-0853 dose levels are 50 mg QD, 150 mg QD, and 200 mg BID, with matching placebos (see [Table 2](#)). Patients will receive GDC-0853/placebo BID, approximately every 12 hours starting on Day 1 and ending on Day 83. Patients should be directed to take one dose (a total of 4 tablets) BID (a total of 8 tablets each day). On clinic visit days, patients should be instructed that study drug will be administered in the clinic.

If a dose is missed, the patient should resume normal dosing with the next scheduled dose. Missed doses should not be taken, as they result in doubling of the dose. Patients should record on the blister wallet (Cohort 1) or bottle (Cohort 2) the dose that was missed and notify study staff of any missed doses. Doses that are vomited will be considered missed doses.

GDC-0853 or placebo may be orally administered with or without food, except for the dose of oral study drug taken at the clinic visit on Days 1 and 28 (see [Appendix 1](#) and

[Appendix 2](#)), which will be administered at the clinic visit while fasting. The dates and times of the most recent prior meal, last dose of oral study drug (prior to clinic visit), and timing of oral study drug administration in clinic should be recorded at each clinic visit. In addition, any use of PPIs, H2RAs, and/or *short-acting* antacids (e.g., Maalox[®], Pepto-Bismol[®], Roloids[®]) should be recorded as concomitant medications, including date and time of last administration *prior to the clinic visit*. Administration of study drug should be staggered with *short-acting* antacid use (i.e., oral study drug should be taken 2 hours before or 2 hours after the *short-acting* antacid).

Table 2 GDC-0853 Dosing Regimen by Treatment Arm (Cohorts 1 and 2)

Arm	GDC-0853 Dose (mg)	No. of Tablets	
		GDC-0853 (a.m./p.m.)	Placebo (a.m./p.m.)
A	50	1/0	3/4
B	150	3/0	1/4
C	200	4/4	0/0
D	0	0/0	4/4
E	0	0/0	4/4
F	200	4/4	0/0
G	0	0/0	4/4

BID= twice daily.

Note: All patients will take 4 tablets BID (i.e., 8 tablets daily) regardless of assigned GDC-0853 dose regimen; therefore, patients may be receiving some placebo tablets as part of their daily dose in order to maintain the blind.

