4.5.9 Electrocardiograms

Triplicate ECG recordings will be obtained at specified timepoints *within approximately 2-5 minutes of each other*, as outlined in the Schedule of Assessments (see [Appendix 1](#) and [Appendix 2](#)).

Pre-dose ECGs acquired on Day 1 and Day 28 should be as closely time-matched as feasible (*morning visits are strongly recommended*), and the patient should be fasting ($\geq 4-8$ hours).

The post-dose ECGs on Day 28 should occur 2 hours (± 30 minutes) after oral study medication is administered, and the patient should be fasting.

ECGs obtained at all other timepoints can be performed without specific restrictions (e.g., may be any time of day, before or after dosing, fasting or fed).

Three interpretable ECG recordings (e.g., without artifacts) must be obtained. The ECG intervals (e.g., PR, QRS, QT, QTcF, and RR) and heart rate from these three ECGs will be entered into the eCRF; in addition, these triplicate readings will be stored for future analysis, if needed.

All ECG recordings must be performed using a standard high-quality, high-fidelity digital electrocardiograph machine equipped with computer-based interval measurements. Lead placement should be as consistent as possible. ECGs for each patient should be obtained from the same machine whenever possible. ECG recordings must be performed after the patient has been resting in a supine position for at least 10 minutes prior to beginning the first ECG recording. All ECGs *should* be obtained prior to other procedures scheduled at that same time (e.g., vital sign measurements, blood draws) *whenever possible*. Body position should be consistently maintained for each ECG evaluation to prevent changes in heart rate. Circumstances that may induce changes in heart rate, including environmental distractions (e.g., television, radio, and conversation) should be avoided during the pre-ECG resting period and during ECG recording.

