- ^g Includes evaluation of the head, eyes, ears, nose, and throat and the cardiovascular, dermatological, musculoskeletal, respiratory, gastrointestinal, genitourinary, and neurological systems. Record abnormalities observed at baseline on the General Medical History and Baseline Conditions eCRF. *The baseline rheumatoid nodules assessment should be recorded in the Day 1 eCRF.* At subsequent visits, record new or worsened clinically significant abnormalities on the Adverse Event eCRF.
- ^h Perform a limited, symptom-directed examination at specified timepoints or as clinically indicated. *After the baseline visit, any new or worsened clinically significant abnormalities should be recorded on the Adverse Event eCRF.*
- ⁱ Triplicate interpretable digital ECG recordings (e.g., without artifacts) will be obtained *within approximately 2–5 minutes of each other*. The ECG intervals (e.g., PR, QRS, QT, QTcF, and RR) and heart rate from these three ECGs will be entered into the eCRF; in addition, these triplicate readings will be stored for future analysis, if needed. ECGs for each patient should be obtained from the same machine whenever possible. ECG recordings must be performed after the patient has been resting in a supine position for at least 10 minutes prior to beginning the first ECG recording. All ECGs are to be obtained prior to other procedures scheduled at that same time (e.g., vital sign measurements, blood draws) *whenever possible*. Body position should be consistently maintained for each ECG evaluation to prevent changes in heart rate. Environmental distractions (e.g., television, radio, conversation) should be avoided during the pre-ECG resting period and during ECG recording.
ECGs *at these specified timepoints* can be performed without specific restrictions (e.g., can be any time of day, before or after dosing, fasting or fed).
- ^k Instructions for ECG collection at the indicated timepoints: before dosing of the *in-clinic* dose on Days 1 and 28 (while patient is fasting) and at 2 hours (± 30 minutes) after dosing of the *in-clinic* dose on Day 28 (while patient is fasting).
PPD should be performed only if QFT is not available. *Refer to the requirements for TB testing in Section 4.1.1 (may be performed within 3 months of screening, if indicated).*
- ^m Not required if documented results of a chest radiograph (read by a radiologist) taken within the 3 months prior to screening is without changes suggestive of active TB infection.

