Appendix 3 Schedule of Pharmacokinetic and Biomarker Samples

Visit	Timepoint	Sample Type
Screening (Day –28 to Day – 1)	No timing restrictions	PBMC protein lysate (U.S. sites only)
		Blood for FACS (U.S. sites only)
		Blood sample for FACS/basophils; (U.S. sites only)
		Serum biomarkers
		Plasma biomarkers
Day 1 ^a	Prior to the dose (to be administered in clinic if applicable), fasting	GDC-0853 PK (plasma)
		PBMC protein lysate (U.S. sites only)
		Blood for FACS (U.S. sites only)
		Blood sample for FACS/basophils (U.S. sites only)
		Serum biomarkers
		Plasma biomarkers
		PAXgene RNA blood
		PG sample (Optional) WGS
Day 7	Prior to the dose (to be administered in clinic if applicable)	GDC-0853 PK (plasma)
		Blood sample for FACS/basophils (U.S. sites only)
		Serum biomarkers
		Plasma biomarkers
Day 28 ^a	Prior to the dose (must be administered in clinic), fasting	GDC-0853 PK (plasma)
		PBMC protein lysate (U.S. sites only)
		Blood for FACS (U.S. sites only)
		Blood sample for FACS/basophils (U.S. sites only)
		Serum biomarkers
		Plasma biomarkers
	PAXgene RNA blood	
	2 h (\pm 30 min) after dosing, fasting	GDC-0853 PK (plasma)
	4–6 h after dosing	GDC-0853 PK (plasma)
	8–10 h after dosing (U.S. sites only) ^c	GDC-0853 PK (plasma)
Days 56	Prior to the dose (to be administered in clinic if applicable)	GDC-0853 PK (plasma)

Appendix 3

Schedule of Pharmacokinetic and Biomarker Samples (cont.)

Visit	Timepoint	Sample Type
Day 84^{a, b}	No timing restrictions unless the patient is entering Study GA30067, in which case collection should occur prior to first dose on Day 1 of Study GA30067	GDC-0853 PK (plasma)
		PBMC protein lysate (U.S. sites only)
		Blood for FACS (U.S. sites only)
		Blood sample for FACS/basophils (U.S. sites only)
		Serum biomarkers
		Plasma biomarkers
Day 140 (Safety follow up visit)	No timing restrictions	PBMC protein lysate (U.S. sites only)
		Blood for FACS (U.S. sites only)
		Serum biomarkers
		Plasma biomarkers
		PAXgene RNA blood
Unscheduled visit	No timing restrictions	PAXgene RNA blood
	Only collect if medically indicated, based on the reason for the unscheduled visit:	GDC-0853 PK (plasma)
		Blood for FACS (U.S. sites only)
		Serum biomarkers
		Plasma biomarkers

Appendix 3

Schedule of Pharmacokinetic and Biomarker Samples (cont.)

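### In Arms A and B, a later-day Day 28 visit times the PK samples and the 2 h ECG from an all-placebo evening dose, so none falls 2 h after active drug

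*Combined protocol and SAP*

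**What the plan says.** - **Section 4.5** prefers morning visits on Days 1, 28 and 84, above all on Day 28. Where a morning is hard to arrange, "patients may be asked to take their morning dose of study drug as scheduled, then fast" for at least 4–8 hours and come later in the day. Pre-dose samples are drawn at that visit, and then "the evening dose of oral study drug will be administered if applicable (e.g., for the Day 28 visit when post-dose blood samples are collected".
- **Section 4.3.2.1, Table 2** gives the active tablets (a.m./p.m.) as 1/0 in Arm A, 3/0 in Arm B and 4/4 in Arms C and F. In Arms A and B the p.m. dose is four placebo tablets. The table note explains that "patients may be receiving some placebo tablets as part of their daily dose in order to maintain the blind". Doses are about 12 hours apart.
- **Appendix 3** has a Day 28 PK sample before a dose that has to be given in clinic, then samples at 2 h (±30 min), 4–6 h and "8–10 h after dosing (U.S. sites only".
- **Section 4.5.9** states: "The post-dose ECGs on Day 28 should occur 2 hours (± 30 minutes) after oral study medication is administered". **Appendix 1, footnote k** anchors the ECGs to the tablets given at the visit; its timing reads "dose on Days 1 and 28 (while patient is fasting) and at 2 hours (± 30 minutes) after dosing of the" (the quote breaks off just before it names what is given at the Day 28 visit). For other visits, "ECGs obtained at all other timepoints can be performed without specific restrictions".
- **Section 4.3.2.1** also requires a record at each visit: "The dates and times of the most recent prior meal, last dose of oral study drug (prior to clinic visit", together with the time of the in-clinic dose.
- **Section 3.3.5** gives the purpose of the Day 28 series as describing absorption, distribution and elimination. **Table 1** lists Cmax and Tmax under a population PK objective, and **Section 6.6** plans a population PK analysis.

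No section makes an exception for the once-daily arms.

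**The concern.** Section 4.5 treats the evening dose as a valid starting point for the Day 28 series. That is true in Arms C and F. In Arms A and B the evening dose contains no drug, so the post-dose series is timed from placebo. This is an authorised route, with Day 28 as its named example, so a site that follows the protocol exactly produces the problem. A blinded site cannot tell which patients are affected, so only the sponsor can correct it.

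Three things are at stake for each affected patient: the earliest scheduled post-dose PK sample in the study, the post-dose ECG meant to accompany it, and the meaning of the pre-dose sample. Section 5.1.1.7 relies on ECGs at PK-matched timepoints, and Section 3.3.5 looks to these data for exposure-response and dose selection. The fasting rule for the Day 28 in-clinic dose also then applies to placebo; the active dose was taken earlier, away from the clinic.

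**Working it through.** **1. Active drug per administration.** Tablets are 50 mg (Section 4.3.1.1). Dose = active tablets × 50 mg, using Table 2:

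- Arm A: a.m. 1 × 50 = 50 mg; p.m. 0 × 50 = 0 mg
- Arm B: a.m. 3 × 50 = 150 mg; p.m. 0 × 50 = 0 mg
- Arms C and F: a.m. and p.m. each 4 × 50 = 200 mg

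These reproduce the doses in Table 2.

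**2. Time since active drug, Arms A and B.** Let g be the hours from the a.m. dose to the in-clinic p.m. dose. Section 4.5 puts the fast after the morning dose and before the visit, so g ≥ 4 on the shortest reading of 4–8 hours. The nominal value is g = 12 (Section 4.3.2.1). The pre-dose sample is at g, and each later measurement is at g plus its nominal time. For a morning visit, the pre-dose sample follows the previous day's a.m. dose by 12 + 12 = 24 h.

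| Visit | Pre-dose sample | Nominal 2 h sample and ECG | Nominal 4–6 h | Nominal 8–10 h (US) |
|---|---|---|---|---|
| Morning | about 24 h | 1.5–2.5 h | 4–6 h | 8–10 h |
| Later, g = 4 | 4 h | 5.5–6.5 h | 8–10 h | 12–14 h |
| Later, g = 8 | 8 h | 9.5–10.5 h | 12–14 h | 16–18 h |
| Later, g = 12 | 12 h | 13.5–14.5 h | 16–18 h | 20–22 h |

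The earliest possible sample is at 4 h and the earliest possible post-dose ECG at 4 + 1.5 = 5.5 h. Both lie beyond 2.5 h. For every permitted gap, the number of PK samples and post-dose ECGs at 2 h ± 30 min after active drug falls from one each to zero.

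**3. Whether another visit replaces them.** In Appendix 3 the Day 1, 7 and 56 PK samples are pre-dose. Day 84, early-termination and unscheduled samples carry no post-dose timing. ECGs outside Days 1 and 28 are unrestricted. Day 28 is therefore the only scheduled source of timed post-dose data.

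**4. What is not lost.** Counting samples within 12 h of active drug at nominal times:

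- Morning visit: 3 (US) or 2 (elsewhere)
- g = 4: 3–4 (US) or 3 (elsewhere)
- g = 8: 2–3
- g = 12: 1, on the boundary

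Once-daily troughs remain available from morning visits on Days 7, 56 and 84.

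**5. How many patients.** Arms A and B have 40 + 110 = 150 patients. All GDC-0853 arms have 40 + 110 + 110 + 60 = 320, and 150/320 = 47%. The documents do not say how many would use the later-day option. Assumed shares, for scale only:

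| Assumed share | Arm A (40) | Arm B (110) | Total | Of 320 |
|---|---|---|---|---|
| 5% | 2 | 5.5 | 7.5 | 2.3% |
| 10% | 4 | 11 | 15 | 4.7% |
| 25% | 10 | 27.5 | 37.5 | 11.7% |

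**The case against.** The best reply is that this is one timepoint, on a discouraged route, in a study whose PK objective is a population analysis. Such a model does not need a 2 h value from every patient: morning-visit patients in Arms A and B, and all of Arms C and F, still inform absorption. The times of the last dose and the in-clinic dose are recorded, and Table 2 shows that the p.m. tablets are inactive, so the samples can be used at their true times. The PK draw and ECG stay paired, because both are timed from the same dose. At a 4 h gap the patient gives at least as many samples within 12 h as at a morning visit. The DAP is not among the documents and may already handle this.

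All of that stands, and it limits the size of the point. It does not remove it: correct time coding cannot supply a 2 h sample or ECG that was never taken, and the readable text does not tell the analyst to treat the p.m. tablets as zero drug.

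A reader might infer more than the documents support:

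- *Peak exposure is missed.* The readable text gives no Tmax or half-life, so it cannot be shown that 2 h is near the peak.
- *Post-placebo values will be tabulated as 2 h values.* No summary by nominal time is planned in the readable text.
- *The Appendix 3 note on holding the dose before a visit contradicts Section 4.5.* It can be read as the dose due at that visit. This is at most a wording point.

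**Conclusion.** The point holds, in a narrow form. For Arm A and B patients who use the later-day Day 28 option, the serial PK samples and the post-dose ECG are timed from placebo, no measurement falls 2 h after active drug, and the pre-dose sample is not a once-daily trough. This rests only on Table 2, the timing rules and a fast of at least 4 h after the morning dose; it does not depend on the assumed shares.

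Severity is minor to moderate. The number affected is unknown and cannot exceed 150 of 320. It would be wrong to conclude that Arm A and B pharmacokinetics are unusable or that the efficacy conclusions are at risk: Arms C and F and the ACR50 analyses do not depend on this timing.

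**What to change.** 1. **Protocol.** Reconcile Section 4.5 with Table 2, Appendix 3, Section 4.5.9 and Appendix 1 footnote k, so that the Day 28 serial PK samples and post-dose ECG are timed from the a.m. tablets in all arms. Applying one rule to every arm keeps sites blinded. The existing ±2-day window for Day 28 can be used to find a morning slot.
2. **DAP.** For any later-day visit that still occurs, compute PK, exposure-response and ECG times from the last active dose, using the recorded dose times and the a.m./p.m. tablet content by arm. Do not class such Arm A or B values as trough or as 2 h post-dose. PK assay staff are already unblinded under Section 4.2, so sites need no new information.
3. **Days 1 and 84.** Do not carry the later-day wording over unchanged. It has patients take a morning dose before the visit, but Section 4.5 makes Day 1 the first day of study drug and Appendix 1 footnote b has no blinded drug given on Day 84. These passages must be reconciled.

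The cost is a short edit to Section 4.5 with matching lines in the schedules, and one DAP rule. The real price is less freedom in scheduling Day 28, which the amendment had deliberately added. If that freedom must stay, item 2 alone corrects the time labels but does not recover the missing 2 h sample and ECG. No change to dose or regimen is proposed.

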4.5.1 Informed Consent Forms and Screening Log

Patients will be screened within a period of up to 28 days prior to administration of study medication to confirm that they meet the entrance criteria for the study. The study investigator or subinvestigator will discuss with each patient the nature of the study, its requirements, and its restrictions.

Written informed consent for participation in the study must be obtained before performing any study-related procedures.

Informed Consent Forms for enrolled patients and for patients who are not subsequently enrolled will be maintained at the study site.

All screening evaluations must be completed and reviewed to confirm that patients meet all eligibility criteria before randomization. The investigator will maintain a screening log to record details of all patients screened and to confirm eligibility or record reasons for screening failure, as applicable.

4.5.1.1 Retesting: Laboratory Inclusion/Exclusion

If a patient does not meet certain laboratory inclusion/exclusion criteria at screening, the investigator may repeat the test once within the screening period (see Section [4.1.2](#) for a list of laboratory tests and levels that can be retested). If the patient meets the laboratory eligibility criteria on the second assessment, he or she will be permitted to enter the study. It will not be considered a retesting if blood samples have to be redrawn because of sample handling problems, breakage, sample integrity, or laboratory error.

4.5.1.2 Rescreening

Rescreening refers to repeating the whole screening process. Rescreening is required if a patient has not met all of the eligibility criteria within 28 days after the original screening visit. (Note: patients who have failed two laboratory testing attempts as described in Section 4.5.1.1 cannot be rescreened, *except in cases where eligibility criteria such as hsCRP have been updated*). Patients are allowed to be rescreened only once. Each patient must be re-consented before rescreening occurs. It will not be considered a rescreening if blood samples have to be redrawn because of sample handling problems, breakage, sample integrity, or laboratory error.

4.5.2 Medical History and Demographic Data

At screening, the following information will be collected:

- **Confirmation of rheumatoid arthritis (RA) diagnosis:** The patient must have a diagnosis of RA based upon the 2010 ACR/EULAR Criteria for RA Diagnosis (see [Appendix 9](#)).
- **Medical history:** The *diagnosis of RA should be recorded on the medical history eCRF (and captured as "rheumatoid arthritis"), including the date of diagnosis. The history must include dates of the most recent vaccinations (specifically influenza, pneumococcus, and zoster) on the eCRF. All medical history relevant to RA will be collected. The medical history should include CHD risk factors per the National Cholesterol Education Program (NCEP) guidelines (e.g., smoking, hypertension, low HDL, family history of premature CHD - see [Appendix 6](#)).*

The medical history must also include clinically significant diseases, surgeries, procedures, cancer history (including prior cancer therapies and procedures), reproductive status, smoking history, and use of alcohol and drugs of abuse.

A detailed history of medication used for RA is required. This should include a complete history of all *conventional synthetic DMARDs and biological DMARDs* ever taken (those taken within 5 years before screening should include dose/duration, date of discontinuation, and reason for discontinuation).

All medications (e.g., prescription drugs, over-the-counter drugs, vaccines, herbal or homeopathic remedies, vitamins, and nutritional or dietary supplements) used by the patient within 12 weeks prior to initiation of study drug are to be recorded.

- **Demographic data:** This data will include age, sex, and self-reported race/ethnicity.

